### **Procedures**

Phase I assessments occur at 0 (baseline), 4-, 8-, and 12-month time points. Veterans will complete an in-person baseline assessment lasting approximately 4-6 hours and a one-year follow-up face-to-face assessment lasting approximately 3-4 hours. All face-to-face assessments will be conducted in private rooms with a white noise machine so that interviews cannot be overheard, although participants may sit in a waiting room to complete their questionnaires (any questions that arise will be answered in a private area). The baseline and annual assessments include clinical assessments, self-report questionnaires, and a hair sample (for biochemical validation of drug use report). Veterans are required to provide a hair sample; thus, Veterans who decline to provide a hair sample decline to participate in the study.

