TBI Assessment Interview	E, PV	✓		✓	This clinician-administered structured interview developed by Vasterling (2008) assesses the number, recency, type of injury, and clinical sequelae associated with traumatic brain injury during deployment. Total number of lifetime head injuries leading to any symptoms will also be assessed. TBI will be assessed at baseline for lifetime history and then re-assessed at the annual interview for any new TBIs that may have occurred during the past year.
Traumatic Life Events Questionnaire (TLEQ)	PV	✓		✓	23 items (Kubany et al., 2000); assesses frequency of exposure to 22 potentially traumatic events encountered outside of military service, resulting in a continuous trauma exposure score. The psychometric properties were carefully established in 5 studies, including a sample of combat Veterans (Kubany et al., 2000).
Deployment Risk and Resilience Inventory (DRRI)	PV	✓		✓	The DRRI (King, King, and Vogt, 2003) is a collection of 13 individual scales assessing pre-deployment, deployment, and post-deployment risk and resilience factors. The DRRI was recently validated for use with OIF Veterans (Vogt et al., 2008). The full DRRI will be readministered at the annual interview if participants have been deployed again. In addition, the social support scale of the DRRI will be re-administered to all participants at Annual 1 in order to obtain an ongoing assessment of social support across time.
RAND Peritraumatic Dissociative Experiences Q.	PV	✓		✓	8 items. Assesses dissociative experiences at the time of a military PTE. Demonstrated good retest reliability ( $r=.85$ ), internal consistency ( $\alpha = .83$ ) and construct validity, and correlated moderately with PTSD symptomatology (Marshall et al., 2002).
Posttraumatic growth Inventory	PV	✓		✓	21 items (Tedeschi & Calhoun, 2005); factors include new possibilities, relating to others, personal strength, spiritual change and appreciation of life.
Full Combat Experiences Scale	PV	✓			34 items. Newly developed and adapted from the DRRI to assess experiences and trauma exposure in land combat situations such as OEF/OIF (Hoge et al., 2004). Will be re-administered if re-deployed.

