PTSD Checklist-5 (PCL-5) Military and Civilian	Med	✓	✓	✓	20 items. Measures symptoms of PTSD during the previous month. Demonstrates high sensitivity and specificity for a CAPS diagnosis of PTSD. Prior research demonstrates the value of including both self-report and clinical interview assessment of PTSD (cf. National Vietnam Veteran Readjustment Study; Kulka et al., 1988).
Schedule of Recent Experiences (SRE)	PV	✓	✓	✓	42 items. The SRE (Holmes & Rahe, 1967) will be used to assess exposure to common, "everyday" stressful life events (e.g., job loss, relationship difficulties, illness or death of a loved one).
Beck Depression Inventory-II (BDI-II)	Med	✓	✓	✓	21 items; The BDI-II (Beck, Steer, Ball, & Ranieri, 1996) is a widely-used measure of depressive symptoms with high internal consistency (Beck, Steer, Ball & Ranieri, 1996) and test-retest reliability (Beck, Steer, & Brown, 1996).
Depression, Anxiety, Stress Scales	Med	✓		✓	21 items; 3 empirically distinct subscales: depression, anxiety, and general stress. Reliable and valid measure of these constructs, and discriminates between anxiety and depression better than other commonly used indices (Antony et al., 1998;

					Brown et al., 1997; Lovibond & Lovibond, 1995)
Columbia Suicide Scale	DV	✓		✓	The Columbia Suicide Scale (Posner et al., 2008) is a state-of-the-art suicide assessment for individuals perceived to be at high risk for suicidality.
Daily Drinking Quest. Revised (DDQ-R)	Med	✓	✓	✓	Yields typical frequency (average number of drinking days per week), typical quantity (number of drinks/drinking day), week sum (total number of drinks during an average week). Binge drinking and tolerance questions added.
Rutgers Alcohol Problem Index (RAPI)	Med	✓		✓	23-items; measures the frequency of physical (e.g., had withdrawal symptoms, passed out or fainted suddenly), psychological (e.g., noticed a change in your personality, felt that you had a problem with alcohol), and social (e.g., caused shame or embarrassment to someone, had a fight, argument, or bad feelings with a friend) consequences experienced during the past three months (White & Labouvie, 1989). Internal reliability for the 23-item RAPI is excellent ( $\alpha = .94$ ; White & Labouvie, 1989).

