Drug Abuse Screening Test (DAST)	Med	✓		✓	20-items to quantify drug misuse. Good internal consistency ( $\alpha = 0.92$ ) and concurrent validity with frequency of drug use over 12-months (Skinner, 1982). Moderately correlated with denial and social desirability. 92% of individuals with drug abuse scored greater than 10.
Fagerstrom Test for Nicotine Dependence (FTND)	DV, Med	✓	✓	✓	6 items that quantify nicotine dependence that exhibits satisfactory internal consistency ( $\alpha = .61$ ), as well as convergent validity with biochemical indices of heaviness of smoking (Heatherton et al., 1991).
Brief COPE	PV	✓		✓	The widely-used Brief COPE assesses a range of behavioral and cognitive coping strategies (Carver, et al., 1989).
Acceptance and Action Questionnaire (AAQ-II)	PV	✓	✓	✓	10 items; The AAQ-II (Hayes, Bissett, et al, 2004) assesses acceptance, experiential avoidance (attempting to alter the form or frequency of unwanted internal experiences), and taking action despite experiencing unwanted private events. Lower scores indicate greater levels of experiential avoidance, whereas higher scores indicate greater experiential acceptance and willingness. The AAQ-II exhibits a single factor structure, good internal consistency (mean $\alpha = .83$ across multiple samples) and test-retest reliability ( $\alpha = .80$ at 3 months, .78 at one year), and convergent associations with symptoms of depression ( $r = -.71$ ), anxiety ( $r = -.58$ ), and global distress ( $r = -.65$ ).
Distress Tolerance Scale (DTS) – Emotional and Physical Distress Scales	PV	✓		✓	16 items (Simons & Gaher, 2005) assessing the extent to which participants can tolerate physical (6 items; e.g., "I'll take fairly extreme measures to stop physical discomfort or pain") and emotional (10 items; e.g., "I usually follow through with tasks that are emotionally upsetting") distress. The ability to tolerate distress may explain why a disorder develops. For example, if one is low on distress tolerance, this may increase risk for reliance on other maladaptive coping strategies, particularly substance misuse.
Brief Resilience Scale	PV	✓		✓	6-item scale measuring resilience (Smith et al., 2008); ability to bounce back or recover from stress. Significantly correlated with 25-item Connor Davidson Resilience Scale.

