Specific Aims 1, 2, and 3, which hypothesize that stress, coping, neurocognition, and psychopathology will predict functioning in returning Veterans concurrently and over time will be initially tested within the context of an independent main effects model in which each of the hypothesized factors will be simultaneously regressed onto the functioning factor while accounting for the covariances among the predictors. Hypotheses will be considered to be rejected if the regression coefficients are either non-significant (i.e.,  $> .01$ ) or are in the opposite direction of our predictions. To test these hypotheses over time, an identical model will be constructed using level of functioning at 1-year follow-up as the primary outcome variable while co-varying for level of functioning at baseline. In addition, a Cross-Lag Panel design (Ecob, 1987; Farrell, 1994; King et al., 2000; Williams & Peodsakoff, 1989) will be employed to examine the autoregressive associations (i.e., the value of interest is assumed to be a function of the previous values plus a random component) and cross-lag associations between the predictors and functional impairment across time. For example, Figure 3 illustrates the structural aspects of a Cross-Lag Panel design based on two waves of assessments of post-deployment stress and functioning. Within this model, we will test the effects of post-deployment stressors from the prior time period on functioning in the subsequent time period, while accounting for the effects of functioning from the prior time period. Likewise we will test the effects of functioning from the prior time period on post-deployment stressors in the subsequent time period, while accounting for the effects of post-deployment stressors from the prior time period. The Cross-Lag Panel design will enable us to examine the possibility that there may be reciprocal relationships that occur over time involving the predictors of interest and functional impairment. Specific Aim 4, which hypothesizes that psychopathology partially mediates the effects of stress, coping, and neurocognition on level of functioning in returning Veterans concurrently and over time, will be achieved by comparing the hypothesized model with several competing models, which include an independent main effects model, a fully-mediated model, and a complete partial mediation model. The overall fit of the hypothesized model will initially be assessed with multiple goodness-of-fit indices including RMSEA, SRMR, CFI, and NFI. Next, chi-square difference tests and AIC values will be used to compare the hypothesized model against the competing models. It is predicted that the hypothesized model will show good overall fit to the model (e.g., RMSEA  $< .05$ , CFI  $> .95$ ) and that the hypothesized model will fit the data significantly better than the competing models. The regression coefficients for the hypothesized indirect pathways will also be examined for statistical significance (i.e.,  $p < .01$ ). The hypothesized model will also be tested over time. Specifically, level of functioning at year 1 follow-up will be regressed on to PTSD-Depression and AUD symptoms at 8-months, which, in turn, will be regressed on to ongoing stress, social support, acceptance, and active coping at 4 months and deployment stress, pre-deployment stress, and neurocognitive functioning at baseline. By testing the hypothesized model in this manner, we will be able to reduce the possibility that response bias during a particular assessment accounts for the hypothesized mediation results. Testing the model in this manner will also take into account the hypothesized causal ordering (i.e., stress, coping, social support, and neurocognition predict psychopathology, which, in turn, predicts functioning).

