
Specific Aim 5, which hypothesizes that changes in the use of healthy coping strategies, social support, post-deployment stress, and psychopathology will predict changes in functioning over time, will be achieved by using latent growth curve models (LGMs) to test hypotheses 5a – 5c. LGMs characterize the trends in growth and change functions for individuals over time (Figure 4). This analytic method assumes that individuals change at different rates and that underlying latent variables determine the overall level and shape of individual trajectories (Lawrence & Hancock, 1998; McArdle, 1998). LGMs can be fit using structural equation models, and are capable of describing the behavior or symptom status of individuals in terms of their initial measurement levels and by their trajectories of change from those levels. LGM techniques can also analyze variability in initial levels and trajectories across persons, while providing means to test the contribution of other predictor variables and constructs as determinants of the different levels and trajectories. LGM techniques offer great flexibility for modeling individual growth

trajectories and their effects on outcomes, while accounting for multiple covariates. LGM will be used to examine the degree to which changes in healthy coping, post-deployment stress, social support, and psychopathology predict changes in functioning over time. It is hypothesized that sustained use of healthy coping strategies and social support, or increases in healthy coping or social support, will predict higher levels of functioning over time, whereas sustained high levels of, or increasing levels of, post-deployment stress and psychopathology are hypothesized to predict lower levels of functioning over time.

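### Phase I's over-time Aim 4 model needs social support and active coping at 4 months, but the schedule has them only at baseline and 12 months, too few waves for a free growth curve in Aim 5

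*Combined protocol and SAP*

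**What the plan says.** All references are to the Phase I part of Completed Phases in the combined protocol and SAP.

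- **Procedures** set four waves: "Phase I assessments occur at 0 (baseline), 4-, 8-, and 12-month time points".
- **Planned Analyses, Specific Aim 4** describe a lagged version of the mediation model. At the outcome end, "level of functioning at year 1 follow-up will be regressed on to PTSD-Depression and AUD symptoms at 8-months". Those 8-month mediators are then regressed on "ongoing stress, social support, acceptance, and active coping at 4 months" and on deployment stress, pre-deployment stress and neurocognitive functioning at baseline. The section gives two reasons for the spacing: to limit response bias from any single assessment, and to respect the assumed causal order.
- **Planned Analyses, Specific Aim 5** "will be achieved by using latent growth curve models (LGMs) to test hypotheses 5a – 5c". The predictors are changes in healthy coping (defined in the hypotheses as acceptance and active coping), post-deployment stress, social support and psychopathology.
- **Phase I Assessment Instruments, DRRI row**: baseline and 12 months are ticked and the 4/8-month column is blank. The row text agrees: "the social support scale of the DRRI will be re-administered to all participants at Annual 1".
- **Phase I Assessment Instruments, Brief COPE row**: baseline and 12 months are ticked and 4/8 months is blank. The description is "The widely-used Brief COPE assesses a range of behavioral and cognitive coping strategies".

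**The concern.** The analysis section assigns each variable in the over-time model to a wave, and for two of them the schedule has nothing at that wave. Hypotheses 4a and 4b make specific predictions about both: active coping fully mediated, social support partially mediated. Those paths have no data in the lagged model as specified.

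The Phase I data now sit in a repository meant for future research. An analyst who follows the text has to choose a substitute without guidance, and the choice matters. Using 12-month scores would place the predictor after the 8-month mediator and at the same visit as the outcome, which defeats both stated reasons for the design. Using baseline scores would not.

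Aim 5 meets the same gap. If change in social support or active coping is to be a growth-curve slope, two waves are too few unless constraints are added that the plan does not mention.

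**Working it through.** **Step 1. Wave needed against wave scheduled (Aim 4 over-time model).**

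| Construct | Instrument in the Phase I table | Scheduled | Needed | Available? |
|---|---|---|---|---|
| Ongoing stress | SRE | BL, 4/8m, 12m | 4m | yes |
| Acceptance | AAQ-II | BL, 4/8m, 12m | 4m | yes |
| Social support | DRRI | BL, 12m | 4m | **no** |
| Active coping | Brief COPE (inferred) | BL, 12m | 4m | **no** |
| PTSD-Depression | PCL-5, BDI-II | BL, 4/8m, 12m | 8m | yes |
| Alcohol | DDQ-R | BL, 4/8m, 12m | 8m | yes |
| Functioning | WHODAS II, QLS | BL, 4/8m, 12m | 12m | yes |

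The exogenous predictors number 4 (at 4 months) + 3 (at baseline) = 7, and 2 of the 7 are missing at the stated wave.

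**Step 2. Could another 4/8-month instrument stand in?** The rows ticked there are contact information, the Treatment Involvement Form, PCL-5, SRE, BDI-II, DDQ-R, FTND, AAQ-II, WHODAS II, Employment Survey and QLS. None is a social support scale or a coping-strategies inventory. AAQ-II measures acceptance, which the hypotheses list separately from active coping. QLS is labelled an outcome. Full-information maximum likelihood cannot help, because a variable unobserved in every participant has no information to recover.

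**Step 3. Is the blank column a PDF artefact?** For the DRRI, no: the row text limits the repeat to the annual visit. The Phase II DRRI row, by contrast, is ticked at every wave and says in words that social support is given at all time points.

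**Step 4. Aim 5: one linear growth curve with T waves.** Observed moments are T(T+3)/2. Parameters are 2 factor means, 2 factor variances, 1 covariance and T residual variances, so T+5, or 6 if the residuals are held equal.

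| T | Moments | Parameters (free / equal residuals) | df (free / equal) |
|---|---|---|---|
| 2 | 5 | 7 / 6 | -2 / -1 |
| 3 | 9 | 8 / 6 | +1 / +3 |
| 4 | 14 | 9 / 6 | +5 / +8 |

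**Step 5. Does joint estimation with functioning rescue it?** Take a parallel-process model with four waves of functioning and check the rank of the Jacobian of the implied moments.

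| Predictor waves | Predictor residuals | Moments | Parameters | Rank |
|---|---|---|---|---|
| 0, 12 months | free | 27 | 20 | 18 |
| 0, 12 months | equal | 27 | 19 | 18 |
| 0, 12 months | fixed at 0 | 27 | 18 | 18 |
| 0, 4, 8, 12 months | free | 44 | 22 | 22 |

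With two predictor waves the model is identified only once the residuals are fixed. At that point the slope is simply a two-point change score.

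**Step 6. What two waves still identify.** Code time in 4-month units, so x0 = I + e0 and x12 = I + 3S + e12, and let F be the functioning slope. Then Cov(S, F) = [Cov(x12, F) - Cov(x0, F)] / 3, which can be estimated. But Var(x12 - x0) = 9 Var(S) + Var(e0) + Var(e12), so Var(S) cannot be separated from the residuals. The covariance of the two changes is identified; the regression of one slope on the other is not.

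**The case against.** **Phase I is closed.** Collection ended in June 2014, the data moved to the repository in November 2021, and the active plan is Phase III, which this point does not touch. The lagged model is also an extra test: the concurrent Aim 4 comparison and the 12-month main-effects models adjusted for baseline functioning remain. All of this stands and lowers the weight. It does not make the specified model fittable.

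**Active coping is not tied to the Brief COPE in the text.** The measurement-model table that the analysis section cites is not among the pages available. The Brief COPE row also has no timing sentence, so that half rests on tick marks. Ticks and text disagree elsewhere: the SDQ row is ticked at baseline and 12 months, yet its description says each time point. This stands as a limit on the active-coping half. No other listed instrument fits the construct, and the social support half does not depend on it.

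**A reader might infer that Aim 5 as a whole fails, or that H5b cannot be tested at all.** The documents do not support that. H5c, stress and the acceptance part of H5a have four waves. The text implies, but does not state, a separate growth curve for each predictor, and the figure it cites is not shown. Step 6 shows that an association between the two changes remains estimable, and fixing the residuals identifies the model.

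**A reader might also infer that alcohol problems at 8 months exist only as drinking quantity and frequency,** because RAPI and the SCID are limited to baseline and 12 months. The DDQ-R row also adds binge-drinking and tolerance questions, is designated a mediator and is ticked at 4/8 months. There is no ground for renaming that mediator.

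**Conclusion.** The Aim 4 over-time model contradicts the Phase I schedule. Two of its seven exogenous predictors have no data at the wave the model names, so it cannot be fitted as written. This is certain for social support and, on the inference that the Brief COPE measures active coping, very likely for active coping.

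In Aim 5 the finding is narrower. An unconstrained linear growth curve for social support (H5b) or active coping (part of H5a) is not identified from two waves (df -2, or -1 with equal residuals). This assumes that the plan means to use each predictor's own slope, which is the natural reading. A constrained two-wave analysis is possible, but the plan would have to say so.

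Severity is moderate to minor. No wave can now be added, no live Phase III analysis is affected, and the main Aim 4 comparison is intact. The text is nevertheless wrong as written, not merely short of detail.

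**What to change.** - **Aim 4 over-time model:** use baseline DRRI social support and baseline Brief COPE active coping, and keep SRE and AAQ-II at 4 months. The order of predictor, mediator and outcome is preserved. State that 12-month scores will not be used as predictors in this model, and name the instrument for active coping.
- **Aim 5:** keep growth curves for acceptance, stress, PTSD-Depression, drinking and functioning. For social support and active coping, use a two-wave change score (baseline to 12 months) and report the result as co-occurring change, not as prospective prediction.
- **Alcohol mediator:** leave it as it is.

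The cost is a few sentences, and all the data needed are on the collection schedule. Because Phase I is complete, date the change and describe it as a correction made after data collection.

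There are two scientific costs. The lag from these two predictors to the 8-month mediator becomes 8 - 0 = 8 months instead of 8 - 4 = 4, so their paths are not on the same lag as those for stress and acceptance, and comparisons of path size should say so. H5b and the active-coping part of H5a also support a weaker claim, because change in predictor and outcome is then measured over the same 12 months.

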## **Aims and Hypotheses**

Specific Aim 1. Identify whether a dose-response relationship exists between level of exposure to stressors and subsequent level of functioning.

*Hypothesis 1a.* Greater exposure to pre-deployment stress and trauma will predict lower levels of functioning concurrently and over time.

*Hypothesis 1b.* Greater exposure to deployment-related stress and trauma will predict lower levels of functioning concurrently and over time.

*Hypothesis 1c.* Greater exposure to post-deployment stressors will predict lower levels of functioning concurrently and over time.

Specific Aim 2. Examine whether potentially malleable resilience factors predict higher levels of functioning in returning OEF/OIF Veterans.

*Hypothesis 2a.* Greater use of healthy coping strategies (i.e., acceptance and active coping) will predict higher levels of functioning concurrently and over time.

*Hypothesis 2b.* Greater levels of social support will predict higher levels of functioning concurrently and over time.

*Hypothesis 2c.* Higher levels of neurocognition will predict higher levels of functioning concurrently and over time.

Specific Aim 3. Examine whether psychopathology predicts lower levels of functioning.

*Hypothesis 3a.* Greater PTSD-Depression symptoms will predict lower levels of functioning concurrently and over time.

*Hypothesis 3b.* Greater AUD symptoms will predict lower levels of functioning concurrently and over time.

Specific Aim 4. Test the theoretical model that psychopathology partially mediates the effects of stress, social support, coping, and neurocognition on functioning concurrently and over time.

*Hypothesis 4a.* The hypothesized model (Figure 1) in which PTSD-Depression and AUD symptoms fully mediate the effects of pre-deployment stress, post-deployment stress, and active coping on functioning and partially mediate the effects of neurocognition, deployment stress, acceptance, and social support on functioning will show significantly better fit to the data compared to any of the following alternative models: an independent main effects model, a fully mediated model, or a full partial mediation model.

*Hypothesis 4b.* PTSD-Depression symptoms will fully-mediate the effects of active coping, pre-deployment stress, and post-deployment stress on functioning and will partially-mediate the effects of deployment stress, acceptance, and social support on functioning.

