A two-step modeling approach will be used to test each aim (Anderson & Gerbing, 1988; Kline, 2005). First, a confirmatory-factor analysis (CFA) measurement model will be computed to determine the degree to which the underlying latent constructs are statistically accounted for by their corresponding hypothesized observed variables. The hypothesized measurement model that we have proposed (see Table 3) is based on a combination of findings from our pilot data, previous research, and current theory and represents our best estimate of what the measurement model will be. If the hypothesized measurement models are supported by CFA, the structural relationships among the latent variables will be tested in the second step. If the initial hypothesized measurement model is rejected, the suggestions for model respecification offered by Kline (2005, pp 165 - 208) will be followed until an acceptable measurement model is found. Once an acceptable measurement model has been identified, the fit of the hypothesized structural model will be assessed with multiple goodness-of-fit indices, including the Root

Mean Square Error of Approximation (RMSEA), Standardized Root Mean Square Residual (SRMR), Comparative Fit Index (CFI), Normed Fit Index (NFI), and the Akaike Information Criterion (AIC). The hypothesized models will also be compared with other competing models using either the chi-square difference test for hierarchically-related models or the AIC for models that are not nested. Alpha will be set conservatively ( $\alpha = .01$ ) for all analyses in order to minimize the probability of Type I error.

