**Power and Sample Size Considerations.** SEM will be used as the analytic strategy for testing all hypotheses. MacCallum, Browne, & Sugawara (1996) describe a method for estimating the required sample size to achieve a given power estimate at specified degrees of freedom ( $df$ ) for both close fitting (i.e.,  $RMSEA = .05$ ) and not close fitting (i.e.,  $RMSEA = .08$ ) models. These  $RMSEA$  values are chosen as points of estimate, since values below .08 are shown to indicate an acceptable but not necessarily close model fit to the data, and values below .05 are shown to indicate an acceptable and close fit to the data (Steiger, 1990; Browne & Cudek, 1993; Hu & Bentler, 1993). The method described by MacCallum and colleagues can also be employed to provide a power estimate for close and not-close fitting models. For the purposes of the current proposal, the software developed by Preacher and Coffman (2006) to calculate power from  $df$ ,  $RMSEA$ ,  $N$ , and alpha using the method described by MacCallum et al. (1996) were used to conduct a power analysis for the proposed study. For SEM equations,  $df$  are equal to the number of observations [i.e., observed variables \* (observed variables + 1) / 2] minus the number of free parameters in the model. Due to the complexity of the proposed models, the  $df$  for our proposed models are high and range from 137 to 922  $df$ , with differences among the models being largely accounted for by differences in model complexity and the number of observed variables included in each model. Power was estimated conservatively by using the model with fewest degrees of freedom to estimate power, as power increases with  $df$  (MacCallum et al., 1996). Setting alpha conservatively at .01, a final sample size of 300 participants (from 400 enrolled) would provide a power estimate of .997 for a close-fitting model with 137  $df$  and .988 for a not-close fitting model with 137  $df$ . In addition, in the event that there is even greater than expected attrition (i.e., attrition rates are greater than 20%), the proposed study would still remain well powered even if as much as 35% of the sample were lost to attrition. For example, leaving alpha set conservatively at .01, a sample size of 195 participants (65% of the original sample size) would still provide a power estimate of .936 for a close-fitting model with 137  $df$  and .822 for a not-close fitting model with 137  $df$ . These results are also consistent with Kline's (2005) rule-of-thumb that sample sizes of 200 or greater are generally well-powered for SEM analyses. Thus, by recruiting an initial sample of 400 participants, we will be well-positioned to retain a sufficiently large sample to remain well-powered throughout the duration of the study, even in the event that attrition rates are higher than expected.

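### Phase I's stated power covers overall model fit only, and two of its decision rules work against Hypothesis 4a: if 4a is true, three concurrent tests pass with probability about .005 and one model comparison cannot be won by the chi-square difference test

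*Combined protocol and SAP*

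**What the plan says.** All of this is in the Phase I part of Completed Phases.

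- **Power.** Power and Sample Size Considerations takes degrees of freedom, RMSEA, sample size and alpha as its only inputs, "using the method described by MacCallum et al. (1996) were used to conduct a power analysis for the proposed study". Degrees of freedom "range from 137 to 922", and the smallest value is used. At alpha .01 it states that "a final sample size of 300 participants (from 400 enrolled) would provide a power estimate of .997 for a close-fitting model", and prints .988 for not-close fit; at N = 195, .936 and .822.
- **Rule for Aims 1 to 3.** Planned Analyses enters stress, coping, neurocognition and psychopathology together as predictors of functioning. "Hypotheses will be considered to be rejected if the regression coefficients are either non-significant" at .01, or if they have the wrong sign.
- **Hypothesis 4a.** PTSD-Depression and AUD "symptoms fully mediate the effects of pre-deployment stress, post-deployment stress, and active coping on functioning". Neurocognition, deployment stress, acceptance and social support are only partially mediated. The model must beat three competitors: main effects only, fully mediated, and full partial mediation.
- **Rule for Aim 4.** The prediction is that the "hypothesized model will fit the data significantly better than the competing models". Models are compared "using either the chi-square difference test for hierarchically-related models or the AIC for models that are not nested". The Aim 4 paragraph also lists AIC values, fit indices and significance of the indirect paths.

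**The concern.** A test of overall fit asks whether a whole model reproduces the covariance matrix acceptably. It does not say how likely a given path is to reach p < .01, or whether one model can be distinguished from another. Those are the questions on which most Phase I hypotheses turn.

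The rules also pull against each other. Aims 1 to 3 require a significant coefficient after adjustment for psychopathology, while Hypothesis 4a says that three of those predictors act only through psychopathology. If the mediation theory is right, the concurrent rule reports three of the plan's own hypotheses as rejected. Printed near a power of .997, such a null coefficient could be taken as well-powered evidence of no effect. The Phase I data now sit in a repository meant for further research, so that misreading could carry forward.

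**Working it through.** **1. Reproducing the printed power.** Inputs from the power section: df = 137, alpha = .01, N = 300 or 195, RMSEA reference values .05 and .08. The null and alternative pair for each test is not spelled out, so pairs were tried. The noncentrality is λ = (N − 1) × df × RMSEA², and power is the noncentral chi-square tail beyond the critical value under the null.

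| N | Null vs alternative | λ null | λ alternative | Critical value | Power | Printed |
|---|---|---|---|---|---|---|
| 300 | .05 vs .08 | 102.41 | 262.16 | 304.01 | .9974 | .997 |
| 300 | .01 vs .05 | 4.10 | 102.41 | 183.73 | .9884 | .988 |
| 195 | .05 vs .08 | 66.45 | 170.10 | 261.12 | .9369 | .936 |
| 195 | .01 vs .05 | 2.66 | 66.45 | 181.87 | .8225 | .822 |

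For example, 299 × 137 × .05² = 102.41. The reverse pair, .05 vs .01, gives .988 at N = 300 but .792 at N = 195, so it does not explain .822. The .01 vs .05 pair explains both. No path coefficient enters any of these figures.

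**2. Concurrent tests of Hypotheses 1a, 1c and active coping in 2a.** Write functioning as Y = bM + dX + other predictors + error, where M is psychopathology and X one of the three predictors. Full mediation means d = 0. The simultaneous model estimates d. With d = 0, a two-sided test at .01 that also requires the predicted sign passes with probability .01 / 2 = .005, whatever the sample size. If the test is one-sided it is .01; the plan does not state sidedness.

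An observed-variable simulation (10,000 runs, N = 300, assumed path sizes) agrees:

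| Predictor | Passes with psychopathology in the model | Passes without it |
|---|---|---|
| Pre-deployment stress | .0045 | .20 |
| Post-deployment stress | .0044 | .33 |
| Active coping | .0046 | .12 |

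The right-hand column depends on the assumed paths. It shows only that a total effect is there to be found, not that power for it is high.

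**3. Hypothesis 4a against the full partial mediation model.** The hypothesized model is that model with the direct paths of three predictors set to zero, so it is nested within it. Removing paths cannot lower the minimized chi-square, so χ²(hypothesized) − χ²(full partial) ≥ 0 always. The difference test can show that the hypothesized model is worse, or not detectably worse. It cannot show that it is better. In the simulation the hypothesized model had the lower chi-square in 0 of 10,000 runs.

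AIC behaves differently. It prefers the hypothesized model when the chi-square difference is below 2 × 3 = 6. If the three paths are truly zero, P(χ² on 3 df < 6) = .888, and the simulation gave .882.

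**4. The remaining coefficients.** Phase I states no effect size. For an assumed partial correlation r with nine predictors in the model, power ≈ Φ(√(N − 10) × r / √(1 − r²) − 2.576).

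| Assumed r | .10 | .15 | .20 | .25 | .30 |
|---|---|---|---|---|---|
| N = 300 | .19 | .50 | .82 | .97 | .997 |
| N = 195 | .11 | .30 | .58 | .83 | .96 |

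This is a range for illustration. The plan uses latent variables, and these are observed-variable approximations.

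**The case against.** The strongest reply has five parts.

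- **The concurrent model is only the first test.** Planned Analyses adds a model of 1-year functioning adjusted for baseline functioning, and a cross-lag panel whose worked example is post-deployment stress. As described, that panel does not contain psychopathology. In the 1-year model, mediation through later psychopathology could leave a non-zero baseline coefficient. Indirect paths are tested as well. This stands. A reader might infer that Phase I cannot support Aims 1 and 2 together with Aim 4, but the documents do not support that.
- **AIC is named for Aim 4.** This stands in part. AIC could favour the hypothesized model, but it is not a significance test, and the general rule earlier in Planned Analyses reserves it for models that are not nested.
- **The basis of the power figure is disclosed.** True, and overall fit is one component of the Aim 4 decision, so the figure is relevant there. But the section opens by covering all hypotheses and ends by calling the study well powered without that limit.
- **The coefficient powers rest on assumed effects.** Agreed. They show sensitivity only. It would be wrong to say that .997 is valid only for unique effects near .30, because the plan never offers .997 as coefficient power.
- **Phase I is finished.** Data collection ended in June 2014, and no misread Phase I result is reported in the documents. This limits the weight of the point but does not correct the rules.

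**Conclusion.** The point holds in a limited form. The four printed values are power for overall fit, and no power is stated for the coefficient, indirect-path or model-comparison tests.

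If Hypothesis 4a is true, the concurrent tests of 1a, 1c and active coping in 2a pass with probability about .005 (.01 if one-sided). The concurrent rule then calls them rejected although total effects exist. The requirement of significantly better fit also cannot be met by chi-square difference against the full partial mediation model. That is one of the three Hypothesis 4a comparisons. The probability of exactly 0 applies to the significance-test reading and assumes that the full partial model contains every path of the hypothesized one.

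A reader might go further and infer that Phase I as a whole has power near zero. The documents do not support this. Neither figure applies to Hypothesis 1b, acceptance in 2a, 2b, 2c, 3a, 3b, the indirect paths of 4b and 4c, or Aims 5 and 6. Power for those is unquantified.

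**What to change.** In Phase I:

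- **Planned Analyses, Aims 1 to 3.** Judge the concurrent parts of 1a, 1c and active coping in 2a on total effects, either from a model without the psychopathology factors or as direct plus indirect effect. State that a null coefficient adjusted for the mediators does not count as rejection.
- **Planned Analyses, Aim 4.** Against the full partial mediation model, define support as a non-significant chi-square difference or a lower AIC. Keep the requirement of significantly better fit for competitors nested within the hypothesized model.
- **Power and Sample Size Considerations.** State that .997 and .988 (and .936 and .822) apply to overall fit only. Coefficient-level power by simulation, the approach the Phase II and Phase III power sections take, would be a useful addition.

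The cost is wording plus one extra model on data already held. The stated power will look less reassuring, and any Phase I conclusion drawn from a null mediator-adjusted coefficient should be re-read. No new data are needed, and Phase III is not affected.
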